The prevalence of FA is estimated to be 25% in the population of urban adult women who have a BMI classification of overweight or obese. Using this prevalence along with a medium effect size, a statistical power analysis was performed for sample size estimation with G\*Power 3.1. The design is a stratified four-group design with a pre and post measurement. Stratification by obesity phenotype (positive or negative for FA) will occur first, followed by random assignment to one of four treatment groups [Information Control (dietary and physical activity instruction), MI alone(diet and physical activity instruction supported by MI), MI((diet and physical activity instruction supported by MI+P(Contrave)). Using an  $f = 0.25$ , an  $\alpha = .05$  and  $\text{power} = 0.95$ , the a priori F test, analysis of variance, omnibus, one-way model gives a projected sample size of 252. As a pilot study, this study is underpowered for statistical hypothesis testing, and analyses will focus on descriptive statistics, estimation of effect sizes, and hypothesis generation and a sample of 40 eligible patients will be enrolled (10 in each group). This meets the pilot study guideline of at least 10% of a fully powered trial and remains realistic in terms of time and cost (Hertzog, 2008) while allowing for 50% attrition. It is expected that 25% of the population will meet the criteria of FA and therefore will need to screen and consent a total of 160 participants to reach the 40 people positive for FA. No more than 160 subjects will be consented for the entire pilot study.

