**Initial Screening for Eligibility (Suicidal Ideation, Pregnancy test (urine test), Lactation, Recruitment):**  
Participants will be recruited from obese patients referred to the Healthy Behaviors Clinic by Regional West Physicians. Nurse researchers who work at the Healthy Behaviors Clinic will inform potential participants about the study and, if they agree to participate, will consent them.

Both treatment groups, Those who test positive for and those who test negative for FA (food addiction) will be assigned to one of four treatment arms, IC, MI, MI+P and P. All will receive dietary and exercise information. After consenting, each participant will be administered the YFAS to determine their obesity phenotype (positive or negative for FA). Participants within each phenotype will be randomly assigned to one of the intervention (MI or MI+P, or P) or the IC information control (diet and physical activity instruction, which will be no less than current standard of care) treatment groups using a randomization schedule (assignments in numbered, sealed, opaque envelopes; one set for each phenotype) 1:1:1:1 ratio, provided by our statistician, [name]. Phenotype assessment and treatment assignment will continue until the sample size (n=10) is met for each phenotype-treatment group category. Those in the control group will be seen at the same time periods as each treatment group to maintain their interaction time with the clinic. They will receive diet and exercise instruction at each time point.

**Intervention Conditions (MI, MI+P):** MI is theorized to decrease a patient's ambivalence and increase his/her perceived behavioral control (self-efficacy) for limiting HPFS and increasing CC intake by emphasizing personal choice and control in decision-making and by affirming the patient's self-management ability. Interventionist nurses will deliver MI sessions following data collection at baseline, 1, 2, 3, and 4 weeks and 2, 3, 4, 5, and 6 months to promote sustained behavioral change. A written MI algorithm will be used to ensure uniform implementation of the intervention.

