#### Data Collection

All research personnel will be CITI-trained. A nursing student will assist the nurse researchers with data collection. Each data collector will undergo fidelity checks (performed by the PI) for each measurement procedure before they will be allowed to collect data. They will also be trained in using the ASA24-2016® dietary recall, so they can assist the patients as needed.

The current version of the YFAS, the YFAS 2.0, will be used to assess participants obesity phenotype (positive or negative for FA). This measure adapts the eleven DSM-5 diagnostic criteria for substance-related and addictive disorders when the substance is HPFS foods. In order to meet the diagnostic threshold on the YFAS, individuals must report at least two of the eleven diagnostic indicators of FA plus clinically significant impairment or distress.

The Automated Self-Administered 24-hour Recall, version ASA24-2016® will be completed at each time point to assess changes in patients dietary intake. This web-based 24-hour dietary recall instrument has been used effectively by hundreds of researchers and has face validity and similar intake results to the AMP.10 A strength of the ASA24-2016® is that it includes most traditional American foods/ingredients.

Height: The patients height will be used in determining BMI and BIA measures. We will use the average of 2 heights (cm) measured with the Seca EC0123 stadiometer. During measurement, patients will be in socked feet with heels placed against the back of the platform and facing straight forward.

Body Composition: Bioelectrical impedance analysis (BIA) will be used to determine body composition. Estimated standard error for BIA is  $\pm$  3.5-5%. We will use a Tanita SC-250 body composition analyzer and follow a standardized protocol to measure percent body fat, body fat mass, fat free mass, percent body water, muscle mass, bone mass, BMI, and visceral fat. The software also classifies patients as underfat, healthy, overfat, or obese based on percent body fat, age and gender.

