Waist circumference: We will use the average of 2 measurements (cm) performed with the patient standing erect with their arms at their sides. Waist circumference will be measured at the uppermost lateral border of the right ilium at the end of normal expiration using an inelastic tape measure positioned around the trunk parallel to the floor. This measure is included because it is a better indicator of body fat and, therefore, health risk than

BMI: In addition, results of a recent study in this population demonstrated that waist circumference has potential as a means of identifying patients with or at risk for obesity and hypertension.

Blood Pressure: We will use the average of 2 blood pressure measurements performed using an Omron HEM- 907 automatic blood pressure monitor. The measurements will be performed while the patient is quiet and still using the appropriate sized cuff placed snugly around the upper arm approximately 2 to 3 cm above the antecubital fossa with the mark on the cuff aligned with the artery.

Determinants of Change Measures: MI Algorithm Questions: These reflect the PCBT determinants of behavior change (the patients perceptions toward limiting HPFS/increasing CC intake). They assess patient attitudes/beliefs (importance score), perceived norms (perceived barriers), and perceived behavioral control/self-efficacy (confidence score). These measures will be recorded by the interventionist nurses during each MI session for their assigned patients.

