#### Statistical Methods to Analyze Data

Missing data will be evaluated. For summated scales on which fewer than 20% of an individuals responses are missing, the individuals mean on the remaining items may be substituted, as appropriate. For analyses requiring complete data, imputation of missing values using the EM algorithm or multiple imputations will be considered, as appropriate. Scoring algorithms for each instrument will be used per the published use manual. Each statistical test will be conducted at  $p=.05$  level. Data will be analyzed using descriptives (means, medians, standard deviations of scores), independent t-tests, correlation coefficients and analysis of variance. In Aim 1, ANOVA will be used to assess differences between the three treatment groups on the YFAS to determined changes in MI confidence, importance and readiness to change scores as well as ASA24-2016® dietary recall and biometric measures. Correlational analysis will be used to explore the relationships between ASA24-2016® dietary recall and biometric measures. In Aim 2 independent t-test will be used to determine if the positive and negative YFAS groups differ across treatment responses.

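### The plan names no method that uses the ten visits and leaves imputation optional despite a 50% attrition allowance, so a completers-only ANOVA would comply; it would lose precision and could bias the month-6 effect sizes

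*Combined protocol and SAP*

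**What the plan says.** The paragraph on intervention conditions sets the schedule: "Interventionist nurses will deliver MI sessions following data collection at baseline, 1, 2, 3, and 4 weeks and 2, 3, 4, 5, and 6 months". That is 1 + 4 + 5 = 10 time points, and the control group is seen at the same times. Under Data Collection, the 24-hour dietary recall "will be completed at each time point to assess changes in patients dietary intake". The motivational interviewing (MI) scores are different: "These measures will be recorded by the interventionist nurses during each MI session for their assigned patients". No such recording is described for the information control (IC) or pharmacotherapy-only arms.

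The sample-size justification, placed under Contribution to Science, reads: "The design is a stratified four-group design with a pre and post measurement". It reports that "the a priori F test, analysis of variance, omnibus, one-way model gives a projected sample size of 252", then reduces enrolment to a pilot of 40, 10 per group, "while allowing for 50% attrition". It calls the pilot underpowered for testing and makes effect-size estimation one of its main outputs.

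The section Statistical Methods to Analyze Data lists its tools: "Data will be analyzed using descriptives (means, medians, standard deviations of scores), independent t-tests, correlation coefficients and analysis of variance". ANOVA serves Aim 1 and an independent t-test serves Aim 2. On missing data it promises an evaluation, permits item-level mean substitution within scales when under 20% of items are missing, and mentions EM or multiple imputation as options to be considered where complete data are required. It gives no imputation model, auxiliary variables, analysis population or sensitivity analysis.

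**The concern.** The methods listed, in their ordinary form, take one value or one change per person. Someone who leaves after month 5 has up to nine measurements on file, but contributes nothing to a month-6 comparison unless that value is imputed. The plan neither requires imputation nor says that it should draw on the earlier visits.

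Two things are at stake. The first is precision: earlier visits carry information about the missing month-6 values, and a completers-only analysis leaves it unused. The second is validity: completers represent all randomised participants only if leaving is unrelated to progress. In a weight programme, people who are not losing weight may be the ones who leave. Because effect sizes are the pilot's stated product, noise or bias in them would pass into the design of a later trial.

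**Working it through.** **1. The plan's own figure.** One-way omnibus F test, f = 0.25, α = 0.05, power 0.95, non-centrality λ = f²N. Three groups give N = 252 (power 0.951), which matches. Four groups give 280, and 252 then has power 0.926. The number of groups is a separate matter. What counts here is that the calculation uses a one-way model in a pre/post design, so the intermediate visits play no part in it.

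**2. Cost of losing half.** The 95% half-width of a two-arm contrast, in SD units, is t(0.975, 2n−2) × √(2/n).
- n = 10: 2.101 × √0.2 = 0.94
- n = 5: 2.306 × √0.4 = 1.46

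The standard error rises by √2 = 1.41.

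**3. How much an all-visit model recovers at month 6.** Assumptions: SD = 1; baseline-to-month-6 correlation r from 0.5 to 0.9, either constant across visits or decaying with time; completely random drop-out spread evenly over the nine follow-up visits and reaching 50% at month 6; covariance known, so this is a best case. Variance × n per arm is:
- completers, change score: 2 × 2(1−r)/0.5 = 8(1−r)
- completers, baseline-adjusted: 2(1−r²)/0.5 = 4(1−r²)
- all visits: generalised least squares with a common baseline mean

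| r | Change | Adjusted | All visits, constant r | All visits, decaying r |
|---|---|---|---|---|
| 0.5 | 4.00 | 3.00 | 2.68 | 2.53 |
| 0.9 | 0.80 | 0.76 | 0.63 | 0.61 |

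Standard-error ratios at the extremes:
- change score against all visits: √(0.80/0.63) = 1.13 to √(4.00/2.53) = 1.26
- baseline-adjusted against all visits: √(3.00/2.68) = 1.06 to √(0.76/0.61) = 1.12

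With no drop-out, the all-visit model and baseline-adjusted ANCOVA have the same month-6 variance (1.50 each at r = 0.5).

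**4. Bias of completers, same rule in both arms.** Simulated BMI with assumed slope SD 0.30 per month, residual SD 0.35, control change −0.5 and true month-6 difference −1.5 kg/m². The odds of leaving at each visit depend on the BMI change observed so far, and roughly half leave.
- random drop-out: −1.51
- odds × 1.35 per kg/m²: −1.45 (3% lost)
- odds × 1.8: −1.37 (9% lost)
- odds × 2.7: −1.21 (19% lost)

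A variant with control change −0.9 and 41–59% drop-out gave −1.42 to −1.04 as the dependence strengthened (5–31% lost). In a further run of this kind, completers ranged from −1.48 to −1.19 under response-related drop-out, while a mixed model gave −1.49 to −1.53.

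**5. Bias under other mechanisms.** Standardised outcome, truth −0.50, r = 0.5 or 0.8, 46–61% drop-out.
- random: −0.50
- poor responders leave both arms: −0.46 to −0.48
- response-related drop-out in one arm only: −0.21 to −0.42
- opposite directions by arm: +0.13 to −0.31

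Sequential regression imputation from earlier visits gave −0.50 to −0.51 throughout. Every mechanism here is missing at random, so this result is expected.

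**6. Dietary recall averaged over follow-up.** With constant r and all nine recalls present, the baseline-adjusted mean has variance (1+8r)/9 − r², against 1 − r² for one adjusted visit.
- r = 0.3: 0.288/0.91 = 32%
- r = 0.5: 0.306/0.75 = 41%
- r = 0.7: 0.243/0.51 = 48%

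**7. Form of time in the model.** Five of the ten visits fall between baseline and week 4, so a straight-line trend is doubtful. For an assumed effect that plateaus, with truth −1.5, linear time gave −1.62 to −1.86 and categorical time about −1.49.

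**The case against.** A reader might infer that the plan discards drop-outs. It does not say so. Imputation is mentioned, and step 5 shows that imputing from earlier visits removes the same bias as a mixed model. What stands is that mentioning an option commits to nothing, and nothing ties the imputation to the earlier visits.

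A reader might also infer that the month-6 contrasts will be biased. The documents do not support that. They give no drop-out mechanism and never name month 6 as the analysis time point. Bias is nil under random drop-out and small under mild dependence that is the same in every arm. A 20% loss needs a steep rule.

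Repeated-measures ANOVA is not excluded, since the one-way label appears only in the sample-size calculation. That is fair, but its classical form also drops anyone with a missing visit.

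The month-6 precision gain over baseline-adjusted ANCOVA arises only through drop-outs. That is true, but 50% attrition is the plan's own allowance. The dietary average does gain with complete data, but it answers a different question from month 6 and gains less when recalls are missing.

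Finally, this is a small pilot that disclaims testing. That limits the consequence without removing it, because effect-size estimation is the stated aim. Small cells rule out an unstructured ten-visit covariance, but not a random intercept and slope pooled over arms, which needs four variance parameters.

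**Conclusion.** The point holds as a gap in specification. The plan collects ten visits, allows for losing half the participants, and neither names a method that uses the intermediate visits nor commits to retaining those who leave.

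A completers-only analysis would comply. Under the assumptions in step 3, its standard error is 13–26% larger than an all-visit model's for change scores and 6–12% larger with baseline adjustment. With a common drop-out rule, attenuation runs from about nil to about 20–30%. Drop-out that differs by arm could do more harm.

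These sizes depend on assumed variances, correlations and drop-out rules. I also assume that the body measurements are taken at every visit, which the documents state outright only for the dietary recall. This is a cheap improvement to make before analysis, not a flaw that invalidates the pilot.

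**What to change.** In Statistical Methods to Analyze Data, for outcomes measured in all four arms, make the main analysis a linear mixed model on all observed visits:
- visit as a categorical factor, not a linear trend
- a common baseline mean across arms within phenotype
- arm × visit, phenotype, and phenotype × visit
- a random intercept and slope per participant, REML, and Kenward–Roger degrees of freedom

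Report each arm-minus-IC difference at month 6 with its 95% CI. For Aim 2, add phenotype × arm × visit with its lower-order terms. Report the month-6 phenotype × arm differences as exploratory estimates with CIs, in place of the pooled t-test. For dietary intake, also report the baseline-adjusted average over follow-up, labelled as a separate estimand. Keep baseline-adjusted month-6 ANCOVA as a sensitivity analysis.

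If ANOVA-type methods remain the main analysis, commit to multiple imputation that uses the earlier visits, plus baseline adjustment. As described, the MI scores are not collected in all four arms, so this model does not cover them.

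The cost is plan wording and some programming, with no extra visits or data. The price is a simple covariance structure and a missing-at-random assumption. Completers-only change scores need a stronger assumption: that leaving is unrelated to earlier response.

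### The randomised arms are to be compared on dietary and biometric outcomes without baseline adjustment and with the dependent variable undefined; ANCOVA on data already collected would usually sharpen the pilot's effect estimates.

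*Combined protocol and SAP*

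**What the plan says.** The sample-size justification, under Contribution to Science, states: "The design is a stratified four-group design with a pre and post measurement". It also says that the pilot is underpowered for testing and will concentrate on description and effect sizes.

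The visit schedule under Proposed methods/approach places data collection at baseline and at each later visit to 6 months. Data Collection has the ASA24 dietary recall completed at every time point. Baseline values of the dietary and biometric outcomes will therefore exist.

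Statistical Methods to Analyze Data lists descriptive summaries and "independent t-tests, correlation coefficients and analysis of variance". For Aim 1, "ANOVA will be used to assess differences between the three treatment groups on the YFAS", and the sentence goes on "to determined changes in MI confidence, importance and readiness to change scores" before adding the dietary recall and the biometric measures. For Aim 2, an "independent t-test will be used to determine if the positive and negative YFAS groups differ across treatment responses". No baseline covariate, ANCOVA or repeated-measures model is named in the document.

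**The concern.** A pre/post design invites three analyses: the final value alone, the change from baseline, or the final value adjusted for baseline. The plan does not say which of the first two its ANOVA uses, and it does not offer the third.

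The choice matters because arms are small. A chance baseline difference between two arms passes into the estimate when final values are compared. When change scores are compared, it is over-corrected, and the over-correction is large if baseline and follow-up are weakly correlated, as is plausible for a single 24-hour recall. The resulting estimates are what a later trial would be sized on.

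**Working it through.** **The plan's own figure.** The projected full-trial size of 252 (f = 0.25, alpha 0.05, power 0.95, one-way omnibus F test) reproduces exactly with three groups (power 0.951). Four groups would need 280, which is a separate matter. The model behind 252 has no covariate and no correlation, so it gives no value of r.

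**Inputs from the documents.** Four arms; 10 per group; 50% attrition allowed, hence 5 completers per arm. Proposed methods/approach sets 10 per phenotype-treatment cell, which gives 20 per arm when the phenotypes are pooled.

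**Assumed.** r from 0.3 to 0.95, with equal SD at baseline and follow-up. Month 6, the end of the intervention, is taken as the post measurement.

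**Chance imbalance.** The SD of a two-arm baseline difference is √(2/n) in SD units:
- n = 5: √0.4 = 0.63; probability of exceeding 0.5 SD is 43%
- n = 10: √0.2 = 0.45; 26%
- n = 20: √0.1 = 0.32; 11%

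Of a baseline difference d, a comparison of final values carries r·d and a comparison of change scores carries −(1−r)·d. For a typical d of 0.45 SD:
- Change scores at r = 0.3 carry 0.7 × 0.45 = 0.31 SD in magnitude.
- Change scores at r = 0.9 carry 0.1 × 0.45 = 0.045 SD.
- Final values at r = 0.9 carry 0.9 × 0.45 = 0.40 SD.

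**Relative variance of an arm difference.** Final value: 1. Change score: 2(1−r). ANCOVA: (1−r²) × [1 + 1/(N−k−2)], where the bracket is the approximate cost of estimating the slope. With k = 4 it is 1 + 1/34 = 1.029 at N = 40 and 1 + 1/14 = 1.071 at N = 20.

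| r | Change | ANCOVA, 10 per arm | ANCOVA against change | ANCOVA, 5 per arm | ANCOVA against change |
|---|---|---|---|---|---|
| 0.3 | 1.40 | 0.937 | 33% lower | 0.975 | 30% lower |
| 0.5 | 1.00 | 0.772 | 23% lower | 0.804 | 20% lower |
| 0.8 | 0.40 | 0.371 | 7% lower | 0.386 | 4% lower |
| 0.9 | 0.20 | 0.196 | 2% lower | 0.204 | 2% higher |
| 0.95 | 0.10 | 0.1004 | equal | 0.1045 | 4% higher |

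Final values have variance 1 throughout. Against them, ANCOVA is about 80% lower at r = 0.9 and 90% lower at r = 0.95, at either arm size.

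**95% confidence interval half-width for a pairwise arm difference (SD units).** These allow for the lost degree of freedom.
- r = 0.5: change score or final value 0.91, ANCOVA 0.80 at 10 per arm; 1.34 and 1.21 at 5 per arm; 0.63 and 0.55 at 20 per arm.
- r = 0.9: change score 0.41, ANCOVA 0.40 at 10 per arm; 0.60 and 0.61 at 5 per arm.

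**The case against.** The strongest reply is that Aim 1 speaks of changes in a design with a "pre and post measurement", so change scores (or the equivalent pre/post group-by-time test) are the natural reading and baseline is already in use. This largely stands. On that reading the 80-90% figure does not apply, and for BMI-like outcomes little imbalance reaches the estimate. But the wording does not fix the dependent variable, and change scores remain inefficient for weakly correlated outcomes.

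A reader might infer that ANCOVA beats both alternatives for every outcome. That is a large-sample result. At 5 completers per arm the penalty removes the gain over change scores at r = 0.9 and reverses it slightly at r = 0.95.

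A reader might also infer that the Aim 2 comparison should simply be baseline-adjusted in the same way. The documents do not support this. Phenotype is assessed, not randomised, so baseline differences between phenotypes may be systematic. Adjusting for them then answers a different question from comparing changes, and the two can conflict. The stated objective is differential response to treatment, which is an interaction.

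Three further points stand. The pilot is declared descriptive. Imbalance is milder if arms are pooled over phenotype (20 per arm). And the motivational interviewing scores are recorded only at those sessions, so no baseline is documented for the information-control and drug-only arms.

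**Conclusion.** The point holds for the randomised Aim 1 comparisons of dietary and biometric outcomes: the dependent variable is undefined and an available baseline covariate is unused. It is a worthwhile, inexpensive improvement. It is not a flaw of validity, since the unadjusted comparison is unbiased under randomisation.

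The size depends on r, which the documents do not give, and on which unadjusted analysis is meant. Against change scores the gain is material at r = 0.3-0.5, small at r = 0.8, and nil or marginally negative at r = 0.9-0.95 with 5 per arm. Against final values it is very large for highly correlated outcomes. The payoff is asymmetric: at 5 per arm, ANCOVA widens the interval by 0.01 SD relative to change scores at r = 0.9 and narrows it by 0.13 SD (1.34 to 1.21) at r = 0.5. One adjusted rule across outcomes of differing correlation is therefore safer than either unadjusted one.

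**What to change.** Add to Statistical Methods to Analyze Data:

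*For each ASA24 and biometric outcome, the month-6 value will be compared across the four arms by ANCOVA with that outcome's baseline value and FA phenotype (the randomisation stratum) as covariates, reporting adjusted arm differences with 95% confidence intervals.*

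This also settles the dependent variable. Where an analysis is confined to one phenotype, the phenotype term drops out.

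For the question of whether phenotypes respond differently, add a phenotype-by-treatment term to the same baseline-adjusted model and report it as an exploratory estimate. With two phenotypes and four arms it uses (2−1) × (4−1) = 3 further degrees of freedom.

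The motivational interviewing scores are outside this change and need their own statement.

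Cost: a few lines of text, and one or two degrees of freedom in the main model. Precision may fall negligibly against change scores for very highly correlated outcomes at 5 per arm. No new data, visits or patients are needed.

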## Study Protocol and Statistical Analysis Plan

### Summary

The purpose of this pilot study is to assess obese clients for two phenotypes, those testing positive and those testing negative for Food Addiction (FA) (Yale Food Addiction Scale, YFAS) and determining the efficacy of four treatments: usual care (IC, dietary and physical activity instruction), individual motivational interviewing alone (MI), individual MI with pharmacotherapy (MI+P) for improving outcome measures within each phenotype, and pharmacological therapy (P).

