#### Proposed methods/approach

Investigators propose assessing obese clients with the YFAS as part of their intake once they are referred to the Healthy Behaviors Clinic by Regional West physicians/practitioners. A nurse researcher with expertise in MI and a nurse practitioner will perform intake assessments, obtain consent and randomly assign participants in each phenotype (positive or negative for FA) to one of three treatment groups (usual care, individual MI alone, and individual MI with pharmacotherapy). Interventions will occur over 6 months. A clinical psychologist with expertise in the YFAS (University of Michigan) will serve as a consultant on this project and a registered dietitian (University of Nebraska Lincoln) will serve as a co-investigator.

Investigators expect that MI and MI+P and P will be more effective in improving outcome measures than IC. We also expect that response to the treatments will differ between the two obesity phenotypes (those testing positive and those testing negative for FA).

To determine if MI alone or MI+P or P is effective in treating obese patients with and without FA (based on the YFAS) as determined by :

- Higher MI confidence, importance and readiness to change scores
- Reduced intake of foods that are highly processed and high in fat and sugar (HPFS) and increased intake of complex carbohydrate foods(fresh fruits, vegetables, whole grains) and minimally processed proteins (nuts, fresh meats) (ASA24-2016® dietary recall)
- Improved biometric measures (BMI, body composition, waist circumference, and blood pressure)

-To determine whether the two obesity phenotypes (with and without FA) differ in their response to the four treatments.

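### Four arms are randomised, but the Aim 1 ANOVA compares three unnamed groups and specifies no difference from the information control

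*Combined protocol and SAP*

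**What the plan says.** **Four arms.** The Summary sets out to study efficacy by "determining the efficacy of four treatments". The Initial Screening for Eligibility section says that participants of both phenotypes "will be assigned to one of four treatment arms, IC, MI, MI+P and P", in a 1:1:1:1 ratio with a separate set of envelopes for each phenotype. The sample-size justification also calls the design four-group, but its bracketed list names only IC, MI and MI+P.

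**Three arms.** Proposed methods/approach has participants assigned to "one of three treatment groups (usual care, individual MI alone, and individual MI with pharmacotherapy". The same section later asks whether the phenotypes "differ in their response to the four treatments".

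**The hypothesis and objective.** Proposed methods/approach states: "Investigators expect that MI and MI+P and P will be more effective in improving outcome measures than IC". Its objective is "To determine if MI alone or MI+P or P is effective in treating obese patients with and without FA", judged on MI ratings, diet and biometric measures.

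**The analysis.** Statistical Methods to Analyze Data says "In Aim 1, ANOVA will be used to assess differences between the three treatment groups on the YFAS". It does not say which three. The section otherwise lists descriptive statistics, correlations and t-tests, and the only use it gives for the t-test is the phenotype comparison in Aim 2. It specifies no contrast with IC and no confidence interval.

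**The concern.** An analysis of three groups in a four-arm trial leaves one randomised arm without its planned comparison, and here the text does not settle which. Two analysts could each follow the plan and report different comparisons.

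Correcting the count alone would not be enough. An omnibus F test asks whether any means differ; it does not estimate how far MI, MI+P or P lies from IC. Those three differences are what the hypothesis is about. They are also the effect sizes a later trial would take from this pilot, which by its own sample-size justification is meant for description, effect-size estimation and hypothesis generation.

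A related gap appears once all four arms enter the analysis. The MI confidence, importance and readiness scores are among the Aim 1 outcomes, yet Data Collection describes the MI question measures as recorded by the nurses during MI sessions. No source is given for them in IC or P.

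**Working it through.** **1. Which arm is missing?**

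| Reading of the three groups | Basis | Arm left out | Comparisons with IC remaining |
|---|---|---|---|
| Usual care, MI, MI+P | The only list attached to that count (Proposed methods/approach) | P | 2 of 3 |
| MI, MI+P, P | Randomisation text that sets the interventions apart from control: "randomly assigned to one of the intervention (MI or MI+P, or P) or the IC information control" | IC | 0 of 3 |

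Four arms give 4×3/2 = 6 pairwise comparisons and three arms give 3, so 3 of 6 are lost on either reading.

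**2. How many participants?** The sample-size justification enrols 40, 10 per group, so one arm is 10 of 40. The randomisation text recruits 10 per phenotype-treatment category: 2×4×10 = 80, so one arm is 20 of 80.

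**3. The plan's own figure of 252.** Inputs from the sample-size justification: one-way omnibus ANOVA, f = 0.25, alpha = .05, power = 0.95. The number of groups entered is not stated. Power is P[F′(k−1, N−k; λ) > F(.95; k−1, N−k)] with noncentrality λ = N·f². The required N is the smallest balanced N with power of at least 0.95.

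| Groups k | N required | Power at that N |
|---|---|---|
| 2 | 210 | 0.9501 |
| 3 | **252** | 0.9515 |
| 4 | 280 | 0.9510 |
| 5 | 305 | 0.9521 |
| 6 | 324 | 0.9513 |
| 8 | 360 | 0.9522 |

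The stated 252 is reproduced exactly with k = 3 (λ = 252 × 0.0625 = 15.75) and with no other k in the table. With k = 4, N is 280 (λ = 17.5), which is 28 more. Keeping 252 with four groups gives power 0.926.

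**4. Precision of the missing contrasts.** Take the SD of change as 1 (so results are in SD units), equal arms of n, and variance pooled over four arms. The 95% half-width for one arm minus IC is t(.975, 4n−4) × √(2/n).

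| n per arm | Where it comes from | Half-width (SD) |
|---|---|---|
| 20 | 80 enrolled | 0.63 |
| 10 | 40 enrolled | 0.91 |
| 5 | 40 enrolled, 50% attrition (40 × 0.5 / 4) | 1.34 |

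These widths come from the sample size and would be wide under any wording. They show what the pilot can deliver once the contrasts are named; they do not measure the harm done by the miscount.

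**5. Does enrolment depend on this?** The plan's guideline is at least 10% of a full trial. 40/252 = 15.9% and 40/280 = 14.3%, so 40 meets it either way.

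**The case against.** The strongest reply is that this is a stale count and not a decision to exclude an arm. The one three-group list omits P, the bracket in the sample-size justification omits P, and 252 is the three-group N. Elsewhere P is fully present: in allocation, in the dosing text, in the hypothesis and in the phenotype objective. On this view any analyst would use all four arms. That is probably how the wording arose, and it makes P the likelier omission; the reading that drops IC is weaker, since the protocol counts usual care among its four treatments. But the current text still says three, names none, and is not corrected anywhere.

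A second reply is that the study is a descriptive pilot, that means and SDs are planned without restriction to three groups, and that contrasts could be computed from them. This is fair, and it makes the 252 versus 280 discrepancy minor. It does not dispose of the main point: the analysis section also plans tests at the .05 level, and an analysis that could be done later is not one that has been specified.

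A third reply is that the source of the MI ratings is a separate measurement gap. It is distinct from the miscount, but it has to be settled with it, because a four-arm analysis of those scores cannot be run without data from IC and P. It is also fair that naming the contrasts leaves the post visit open: sessions run to 6 months, and a 12-month measure is also planned.

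**Conclusion.** The plan is wrong as written and must be corrected. Taken literally, the Aim 1 ANOVA omits one of four randomised arms: 10 of 40 participants, or 20 of 80 if the cell size in the randomisation text applies. If the omitted arm is P, which is likelier, P versus IC has no Aim 1 analysis; if it is IC, none of the three hypothesised comparisons has. On either reading no difference from IC is specified.

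The arm count and the missing contrasts follow from the text alone. That 252 came from three groups is an inference from back-calculation, though an exact one. It is secondary, because it does not drive the enrolment of 40. The half-widths of 0.63 to 1.34 SD assume equal arms, a common SD of change and, for the widest, attrition spread evenly over the arms.

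**What to change.** **Required**

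- In Proposed methods/approach and in Statistical Methods to Analyze Data, replace three with four treatment groups and name them: IC, MI, MI+P, P. Add P to the bracketed list in the sample-size justification.
- State that Aim 1 reports MI minus IC, MI+P minus IC and P minus IC in pre-post change, each with a 95% confidence interval, for every dietary and biometric outcome. Name the visit that counts as post.
- For MI confidence, importance and readiness, choose one: (a) ask the same rating questions in IC and P; or (b) limit that analysis to MI and MI+P, and amend the objective that uses these scores to judge P.
- Minor: restate 252 as 280, or state that 252 gives 92.6% power with four groups.

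**Optional, and separate from the error**

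- Adjust the contrasts for the baseline value. The gain depends on the pre-post correlation, which the documents do not give, and may vanish in a small sample if that correlation is very high.
- Report the arm-by-phenotype difference with a confidence interval for Aim 2. First reconcile the sample-size justification, under which all 40 may be FA-positive, with the randomisation text, which fills both phenotypes. With n per cell and SD of change 1, the standard error is √(4/n): 0.63 at 10, 0.89 at 5 and 1.26 at 2.5 (20 completers over eight cells). It cannot be estimated if all 40 are FA-positive.

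**Cost.** The changes are to wording in three sections. Dietary and biometric outcomes need no new data, and enrolment is unchanged. Option (a) adds a few questions in IC and P at up to 10 visits, and may expose those arms to part of the MI method, because the nurses use the ratings to open the MI discussion. Option (b) needs no data, but gives up that objective for P and any comparison with IC on these scores. The intervals versus IC will be wide and should be reported as such.
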